Daily habits (or routines) are a commonly reported strategy for maintaining high medication adherence among patients who successfully manage chronic diseases [15,16], but forming new routines is often difficult for patients to do on their own. According to recent psychology research, it takes approximately three months of repeatedly performing a daily behavior in response to the same contextual cue [17–20], as outlined in the Habit Formation Model in Figure 1a [21], before the behavior becomes routinized. Once routinized, the cognitive processes that govern the behavior move to neurological systems that operate non-consciously [22–25]. Additionally, behaviors that are routinized no longer require high intrinsic motivation to be carried out, and thus can enable even the most vulnerable ART treatment initiators, such as those with limited motivation, to maintain high long-term adherence.

[figure not shown]

Figure 1: Duhigg's (2013) habit formation model underlies the anchoring intervention strategy, which we propose to enhance in INMIND through incentives and reminders to successfully routinize ART adherence among HIV-patients.

One common intervention method for establishing new routines is to anchor the targeted behavior to an existing routine that acts as the contextual cue. For example, taking ART medication after brushing one's teeth in the morning or after completing evening prayers. This method is often called Anchoring (Figure 1b), and has been shown to be an effective intervention for promoting physical activity routines [26], improving dietary routines [27], and maintaining smoking cessation [28]. However, these existing studies typically enrolled participants with high intrinsic motivation for the targeted behavior [29–33], and therefore hold little potential for real-life clinical situations where there is no extra support for individuals with low intrinsic motivation (as is typical for many patients in HIV care [34]). Moreover, less than half of participants in these existing studies successfully used their anchor and maintained the desired behavior in the long run [35].

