Behavioral economic theory demonstrates the need for ongoing support during the time it takes to complete the routinization process and also provides proven intervention methods for delivering such support to enhance existing anchoring interventions. The behavioral economic biases of lack of salience of ART adherence (e.g., over time, more pressing needs of daily life dominate one's attention and focus) and present bias (e.g., excessively undervaluing the future health benefits of one's actions) help to explain why many people have trouble sticking to their healthy intentions [36,37]. Fortunately, behavioral economics also suggests two methods for countering these biases: 1. text messages that can be used to reinforce information provided at recruitment and to increase the salience of the anchoring routinization strategy, and 2. small behavioral economics-based incentives that have successfully changed a range of health behaviors by countering present bias [38–41]. Therefore, this study will test whether incentives for linking daily pill-taking to the timing of an existing routine behavior can establish and maintain high ART adherence routines in a feasible and scalable manner.

Additionally, this intervention is being targeted to treatment initiators in order to leverage the 'fresh start'-effect [45], a period of heightened motivation and attention. ART adherence instructions are initially salient for treatment initiators, but over time they fade from attention. Among HIV-infected adults in Sub-Saharan Africa, forgetfulness is the most frequently reported adherence barrier to maintaining high long-term adherence [46,47]. Treatment initiators may therefore need subsequent support for adhering to the ART medication protocol until the behavior has been successfully routinized, which will be provided in the form of text messages and incentives.

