Apart from the patient-facing work, Mildmay also provides technical assistance to organizations and governments, hosting training and educational courses for over 1,500 professionals per year. Further, the Mildmay Uganda laboratory is accredited by the South African National Accreditation System under ISO 15,189:2012, and specializes in virology and other tests.

Mildmay also has numerous ongoing research projects involving international researchers. It has a standing Community Advisory Board comprising of church leaders, elected councilmen, healthcare providers (external to Mildmay), and HIV client advocates.

Sampling Strategy

The objective of this study is to establish preliminary efficacy as well as acceptability and feasibility of the interventions. Consequently, 150 participants will be recruited from Mildmay's main site for the pilot study. The sample will be representative of the patient population at Mildmay with a roughly 70:30 ratio of female to male clients.

Electronic medical records and the hospital electronic database will be used to screen the client population for initial eligibility based on age and ART initiation period, as noted in the Eligibility Criteria below. For this step, the hospital staff (and not the study coordinator) will mine the electronic database for this information to create a master list of eligible clients. Given the focus on treatment initiators, this process will be carried out weekly to identify newly diagnosed clients who are eligible to participate in the study.

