A daily list of expected clients will be generated from the master list for the study coordinators to locate those deemed eligible and who are due for a clinic visit. Once a client is located, a pre-baseline visit will be initiated with the study coordinator approaching the client and inquiring about their interest in participating in an ongoing study. On confirming interest, clients will be taken to a separate study room to verify their eligibility, and to receive their consent to participate. Consented participants will be given a medication event management system (MEMS) cap and instructed to store one of their HIV medications in a pill bottle with the MEMS cap attached. Additionally, they will be given a study appointment after approximately one month of this initial visit for adherence data retrieval and baseline survey administration. The first month of adherence data will be used as a baseline and the intervention will not begin before this follow-up visit.

Inclusion Criteria

The study sample will consist of male and female clients aged 18 and older who have started ART at Mildmay within the preceding three months. Treatment initiation is an important eligibility criterion given the conceptual framework of the pilot, which suggests that habit formation during initiation is a key driver for sustained ART adherence over time. Based on electronic records

data from Mildmay, each month at least 100-150 clients with these characteristics begin treatment at the hospital (for a total of 1,758 in 2018); therefore, a large pool of potentially eligible clients will be available for recruitment. Given the nature of the intervention, inclusion will also require participants to own, or have access to a phone at least five days a week throughout the duration of the intervention, while being willing to receive text messages throughout the intervention period.

Exclusion Criteria

Children under the age of 18 were excluded for two reasons: 1) the pediatric clinic is separate from the main recruitment site (which primarily caters to adult clients), and 2) the intervention might require alteration to account for the specific needs of children and adolescents.

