Feasibility and acceptability will be analyzed using summary statistics derived directly from our self-reported measures. To estimate preliminary efficacy, statistical analyses comparing group-level differences in the secondary and tertiary outcome measures will be performed. An Analysis of Covariance framework will be used to test for group differences in each secondary and tertiary outcome, controlling for the participant characteristics that are found to differentiate the groups at baseline. For analyses of dichotomous variables, such as viral suppression, a non-parametric McNemar's test and an analogous multiple logistic regression will be used to control for covariates to assess group differences. In addition to static comparisons of group means for each outcome at three-month intervals, the longitudinal nature of the data will be leveraged by using repeated measures and time-series techniques. Specifically, a linear mixed model with repeated observations will be fit using maximum likelihood through 'xtmixed' in the

software package Stata to study group-level temporal dynamics in daily measures of the primary and secondary outcomes.

Sample and Effect-size Estimation

We will recruit a total of 150 participants and will assume a 90% retention rate through the 9-month study period. This is a conservative estimate of attrition, as previous research in the same clinic and with a similar population observed only 6% attrition over 12-month study periods [44,48]. Given the study objectives of establishing acceptability, feasibility, and preliminary effectiveness, the targeted sample size may not have the power to detect many of the effects that would be clinically significant. Nonetheless, effect size calculations associated with 80% power (2-tailed test) with regard to the primary outcomes at month nine have been carried out. A recent study conducted at Mildmay suggested that mean ART adherence rates are ~ 75% (SD = 20) as measured by MEMS caps [44]. Using these parameters as estimates of adherence for the control group, and 10% attrition at month nine, a sample size of 150 will provide sufficient power to detect a 9% difference in mean adherence between the pooled intervention groups and the control group (effect size = .47), and a roughly 11% difference in mean adherence between the two intervention groups. This translates to the study being able to detect medium effect sizes.

Qualitative Analysis

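### Texts and prizes start about 1 to 4 months after ART start, yet time on ART is neither a pre-specified covariate nor part of how the studied population is described

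*Combined protocol and SAP*

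**What the plan says.** The introduction explains why initiators were chosen. The intervention is "targeted to treatment initiators in order to leverage the" fresh-start effect, described as a time of raised motivation and attention, with no length given. The same paragraph says that attention to adherence instructions fades, so initiators may need further support until pill-taking is routine. Earlier, the introduction says of habit formation that "it takes approximately three months of repeatedly performing a daily behavior in response to the same contextual cue" before the behavior becomes routine.

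The Inclusion Criteria admit "clients aged 18 and older who have started ART at Mildmay within the preceding three months" and justify this by the importance of forming the habit during initiation. Under Sampling Strategy, consenting participants receive a MEMS cap and "they will be given a study appointment after approximately one month of this initial visit". The section then adds: "The first month of adherence data will be used as a baseline and the intervention will not begin before this follow-up visit". Study Design gives three months of intervention, counted from the baseline survey.

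Sampling Strategy says clinic staff use the records to "screen the client population for initial eligibility based on age and ART initiation period", repeated weekly. Statistical Methods and Analyses describes an ANCOVA "controlling for the participant characteristics that are found to differentiate the groups at baseline". It also describes a linear mixed model for the daily measures, for which no covariates are listed. Comparison to prior work names age and sex for the impact analysis. Time on ART is not named in any analysis.

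**The concern.** The plan selects people by how recently they started ART and gives reasons that depend on that recency. The entry window and the baseline month together then produce a wide spread in time on ART when support begins. Some participants may receive their first text a month after starting ART, and others four months after.

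On the plan's own account, attention to adherence instructions changes over this period. Time on ART is therefore a plausible predictor of adherence and a plausible modifier of the intervention effect. The covariate rule treats it like any other characteristic: it enters only if a chance imbalance appears, and never as a modifier.

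Two things are at stake. A conclusion worded as being about treatment initiation would describe the population less exactly than the data allow. And the pilot, which is meant to inform a larger trial, would not report how long participants had been on ART when support began.

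**Working it through.** The plan gives no figure for time on ART at intervention start, so there is none to reproduce. Its one design calculation (Sample and Effect-size Estimation) supplies only the SD and sample size used in step 4.

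**1. Range of time on ART when the intervention starts**
- Time on ART at enrolment: 0 to 3 months (Inclusion Criteria).
- Lag to the baseline survey: about 1 month (Sampling Strategy).
- Start = enrolment time + lag, so 0 + 1 = 1 month up to 3 + 1 = 4 months.
- End = start + 3 months of intervention, so about 4 to 7 months.

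**2. Share starting after month three**

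Share = P(enrolment time > 3 − lag). The documents give no enrolment distribution, so each line below is an assumption. The lag is 1 month unless stated, which makes the share P(enrolment time > 2).
- Everyone enrolled within two months of ART start: 0%.
- Early-weighted, 3 × Beta(1,2): (1/3)² = 11%.
- Uniform on 0 to 3 months: 1/3 = 33%, or 50 of 150; mean start 1.5 + 1 = 2.5 months.
- Late-weighted, 3 × Beta(2,1): 1 − (2/3)² = 56%.
- Uniform with a lag of 0.75 months: 0.75/3 = 25%. With a lag of 1.5 months: 1.5/3 = 50%.

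These values illustrate a range and are not bounds. The threshold also matters if enrolment falls on monthly visits. Consent in equal shares at months 1, 2 and 3 gives starts at months 2, 3 and 4. One third is then beyond month three, but two thirds are at month three or later.

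**3. Does the analysis use time on ART?**
- The variable exists. Eligibility depends on having started ART within three months, and the records are screened on the initiation period. I therefore take the start date to be on file.
- The ANCOVA rule would admit it only if it differed between arms.
- No interaction or descriptive summary by time on ART is named.

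**4. What an arm-by-months estimate could show**
- Inputs: SD 20; 150 × 0.90 = 135 retained; 1:1:1 allocation, so 45 control and 90 pooled intervention. Assumption: uniform time on ART, with SD √(9/12) = 0.866 months.
- SE of the pooled difference: 20 × √(1/45 + 1/90) = 3.65 points.
- SE of the difference in slopes: 3.65/0.866 = 4.2 points per month; 95% half-width 1.96 × 4.2 ≈ 8.3.
- If enrolment were uniform over only 0 to 2 months (SD 0.577), the SE would be 3.65/0.577 = 6.3.

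Against the plan's stated detectable difference of 9 points for the whole comparison, this is too imprecise to settle any claim.

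**The case against.** A reader might infer more: that a third or more of participants are treated after the window the trial is meant to test. The documents do not support that, for three reasons.

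- The three months in the introduction count repetitions to one cue, not time since ART start. Participants choose their anchor within the study, and three months of support from the baseline survey matches that count. The Control Group section puts the choice of anchor at recruitment, while the Messages Group section puts it when assignment is revealed. Those passages need reconciling, but neither starts the count at ART start.
- The fresh-start period has no stated length, and the same paragraph argues for later support because attention fades. Support that begins some weeks into treatment fits that argument.
- No enrolment distribution is given. Weekly screening for newly diagnosed clients could bring enrolment forward, and approaching clients only when a visit is due could delay it. One third is therefore not a floor.

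A reader might also infer lost power. As a labelled hypothetical, suppose a 10-point effect is halved for one third of participants. The average effect becomes 10 × 2/3 + 5 × 1/3 = 8.3 points, and power falls from 78% to 62% (SD 20, 45 against 90, two-sided 0.05 assumed). Nothing in the documents supports such a halving. Randomization protects the arm comparison, and the trial still estimates the average effect in the population it enrolled.

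It is also fair to say that the baseline automaticity index and the baseline MEMS month measure existing routine more directly than months on ART. However, the plan names no moderation analysis with them.

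These objections remove the window claim, the one-third floor and the power loss. They leave the 1 to 4 month range, and they do not supply a pre-specified role for time on ART.

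**Conclusion.** The point holds in limited form. The intervention begins about 1 to 4 months after ART start. This follows directly from the plan and rests only on the approximate one-month lag. The share beyond month three is unknown, and the 33% and the 0% to 56% are results of assumed distributions. The documents set no cut-off at three months, so no one can be called treated too late.

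The issue is how the population is described and whether the effect might vary with time on ART. Bias between arms is not in question. The gap in the analysis is modest: a variable that the plan's own reasoning makes relevant, and that screening already uses, would enter only by chance imbalance. This merits a short change to the analysis plan but no change to the design.

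**What to change.** - Derive months on ART at the baseline survey from the ART start date in the clinic record, and report its distribution by arm.
- Enter it as a pre-specified covariate in the ANCOVA and mixed models for Primary Outcomes 1 to 4, whether or not the arms differ on it. Name those outcomes explicitly, because the ANCOVA sentence refers to secondary and tertiary outcomes.
- In the conclusion, describe the studied population as patients about 1 to 4 months after ART start, refined by the observed distribution.
- An arm-by-months-on-ART estimate with its confidence interval may be added as description only. With an SE of about 4.2 points per month, no claim should depend on it. An analysis restricted to those within three months of ART start is not needed, since the documents give no basis for that cut.

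The Results section says data collection is complete and analyses are ongoing, and the plan has the impact analyst blinded to assignment. The change should be recorded before that analyst sees allocation; if that has already happened, the adjustment should be labelled post hoc.

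The cost is one variable that should already be on file, one model degree of freedom and a slightly narrower claim. Eligibility, the baseline month and the interventions stay as they are.

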Participants assigned to this arm will receive care as usual, including the adherence support mechanisms that are part of usual care practices. At recruitment, participant will be educated about the importance of pill-taking using a leaflet that details information on how to establish healthy pill-taking routines. Participants will then be asked to select one of the following three pill-taking anchors: getting dressed in the morning, eating a meal (breakfast) in the morning, or eating dinner in the evening, which will also be described in a habit leaflet, and they will be asked to specify the time at which their anchor typically occurs. Once selected, participants will be asked to continue using their MEMS caps and to bring the caps during the next visit.

During each of the subsequent study visits, scheduled roughly one month apart during the intervention period and 1-3 months apart subsequently, participants will be asked a short questionnaire inquiring about changes in their ART adherence behavior, including any changes in location, times, and social activities surrounding their pill-taking behavior and their ART adherence habit strength. They will also be asked about any clinical changes to their ART regimen, as well as about their daily MEMS cap usage. This is because pill-pocketing (dispensing of more than one dose in a given bottle opening event) is a common phenomenon among the population, with 15% of a previous study sample reporting pocketing [48]. If participants indicate pocketing, the study coordinator will work with the participant to find another solution to avoid pocketing and continue using their MEMS cap, and we will adjust for their pocketing in our assessment of their adherence outcomes. Finally, participants will be asked about any changes to their contact information or addresses, and updates will be noted in the contacts data.

The study coordinator will then download the readings from the MEMS cap, inquire about the participants' next visit, and remind them to continue taking their pills on time. This procedure will be carried out throughout the intervention and post-intervention periods.

Treatment Group 1: Messages Group

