period. Upon revealing their group assignment, participants will be registered on the Twilio platform following the same procedures as outlined for the *Messages* arm. Participants will also be informed that if at their next visit they have taken their medication on 70% or more of the last 30 days within +/- one hour of their chosen anchor time, then they will be eligible to participate in a lottery to win mobile airtime. The study coordinator will note that they will receive three opportunities to participate in the lottery (i.e. at each study visit over the next three months, if they are eligible). To ensure participants understand the process, the study coordinator will carry out a mock prize drawing wherein participants will choose from one of three cards listing an airtime prize amount. The chosen card and corresponding prize will be revealed to the participant, and the amount listed on the card will be sent to the participant's phone number (via Reloadly) in the form of a mobile top-up balance.

During each subsequent study visit, the study coordinator will check the client's MEMS cap data and fill out a form that asks questions about adherence behaviors (as with the control group), and text messages (as with the *Messages* group). The study coordinator will also ask about pill pocketing to assess prize eligibility. To avoid unfairly punishing participants who pocket doses (resulting in an under-reporting of MEMS data in the software), participants will be asked about an estimated number of doses pocketed and will be allowed to enter one wild card prize drawing when they did not reach the adherence threshold. They will be specifically informed that this will be a one-time exception. After the three-month intervention, participants will follow the same procedures as the Control and *Messages* groups.

MEMS-cap procedures

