MEMS-data will be collected continuously over the course of the three-month intervention period allowing for mean adherence assessment during the intervention period. Specifically, the number of pill bottle openings detected by the MEMS cap will be used as a measure of each participant's pills taken per day. Mean adherence will then be calculated as the number of pills taken per day during the intervention period, divided by the number of pills prescribed during the intervention for a given participant (i.e., # of actual bottle openings / # of prescribed bottle openings). This mean adherence measure will be capped at 100%, meaning that any pill bottle openings over the participants' number of prescribed daily pills will be ignored. In this way, the mean adherence measure will range from 0 to 100 and will be calculated for each participant on each day of the intervention period. Only one of the daily ART medication doses will be used to calculate the primary mean adherence variable. Both the mean adherence over the three-month intervention and a monthly measure of mean adherence will be calculated and analyzed.

Primary Outcome 2: Electronically measured mean medication adherence post-intervention

Post-intervention, MEMS data will be collected continuously for six months to investigate post-intervention mean ART adherence ('persistence'). The calculation of this outcome is the same as that of *Outcome 1* except for the timeline over which the data will be collected and analyzed.

Primary Outcome 3: Routinization of ART adherence during intervention

In addition to *Outcomes 1 and 2*, a novel measure of routine adherence will be assessed during the intervention period. The novelty of the measure is in that it is explicitly based on the temporal pattern of pill-taking. The measure will be calculated as the fraction of scheduled pills taken within a two-hour window (+/- one hour) around the typical time that participants report completing their existing routine behavior that anchors their pill-taking. This measure provides an objective way for determining the behavioral automaticity of pill-taking, and will be calculated as the mean of all prescribed pills taken around participants' anchor time over the three-month intervention.

Primary Outcome 4: Routinization of ART adherence post-intervention

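### Primary adherence is openings-only in one section and pocketing-adjusted in another, and in months 1 to 3 pocketing reports are tied to a prize in the Incentives arm only

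*Combined protocol and SAP*

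**What the plan says.** Under Primary Outcome 1, "the number of pill bottle openings detected by the MEMS cap will be used as a measure of each participant's pills taken per day". The formula is the number "of actual bottle openings / # of prescribed bottle openings", and the cap at 100% is explained by saying that "any pill bottle openings over the participants' number of prescribed daily pills will be ignored". For Primary Outcome 2, "The calculation of this outcome is the same as that of *Outcome 1* except for the timeline". Pocketing appears in neither definition.

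The section Control Group: Usual Care explains that participants are asked about cap use because several doses may be removed at one opening, "with 15% of a previous study sample reporting pocketing". It then says that, where participants indicate pocketing, "we will adjust for their pocketing in our assessment of their adherence outcomes". It does not say whether this means adding doses, dropping days or using a covariate. Neither Statistical Methods and Analyses nor Handling Missing Data and Attrition mentions it.

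The section Treatment Group 2: Incentives Group carries over the control-arm questions and adds three things: the pocketing question serves to decide prize eligibility, an estimate of the number of pocketed doses is requested, and participants "will be allowed to enter one wild card prize drawing when they did not reach the adherence threshold". They are told this happens once only. After month three, all arms follow the same procedures.

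**The concern.** Two analysts following this plan could compute different primary outcomes. One would use openings alone. The other would let self-report into a measure that the plan labels as electronically measured.

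The second version matters more because the motive to report differs by arm. Participants and interviewers know the assignment (Randomization and Allocation), and only in the Incentives arm can a pocketing report help a participant who missed the threshold. If reported doses are credited as taken, extra reporting in that arm appears as extra adherence. Limitations acknowledges that openings may be manipulated in the Incentives arm but does not mention inflated pocketing reports. While both versions remain open, the primary estimate is also not fixed in advance.

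**Working it through.** **1. The plan's own benchmark.** From Sample and Effect-size Estimation: 150 recruited, 90% retained, 1:1:1, so 150 × 0.9 / 3 = 45 per arm and 90 in the pooled intervention arms; SD 20; 80% power, two-sided. Alpha is not stated, and 0.05 is assumed. Detectable difference = (1.960 + 0.842) × SD × √(1/n₁ + 1/n₂).
- Pooled against control: 2.802 × 20 × √(1/90 + 1/45) = 10.2 points (0.51 SD). The plan states 9 points (0.47).
- One arm against another: 2.802 × 20 × √(2/45) = 11.8 points. The plan states roughly 11, for the two intervention arms.

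The plan's figures are not reproduced. That is a separate matter, and the recomputed values serve here only as yardsticks.

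**2. Does the choice of definition matter without any arm difference in reporting?** Shift in an arm's mean = share reporting × percentage of days credited. The 15% is the plan's figure; 5–30% of days credited is assumed.
- 0.15 × 5 = 0.75 points; 0.15 × 30 = 4.5 points.

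So the two definitions can differ by 0.75 to 4.5 points in every arm. With equal reporting and equal credit, the difference between arms is 0.

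**3. Unequal reporting.** Assume 15% report in the other arms, 30% report in the Incentives arm, reporters are credited 10–30% of days, and there is no true effect.
- Incentives against another single arm: (0.30 − 0.15) × 10 = 1.5 points; (0.30 − 0.15) × 30 = 4.5 points. Against 11.8 this is 13% to 38%. With SE = 20 × √(2/45) = 4.22, the two-sided false-positive rate rises from 5% to between 6.5% and 18.7%.
- Pooled against control: Incentives is 45 of the 90, so the gap halves to 0.75–2.25 points. Against 10.2 this is 7% to 22%. With SE = 20 × √(1/45 + 1/90) = 3.65, the rate is 5.5% to 9.5%.

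**4. One wild card only.** If extra reporting affects one of the three months, the three-month gaps are divided by 3: 0.5–1.5 points for a single-arm comparison and 0.25–0.75 points pooled.

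**5. Outcomes 3 and 4.** These count pills taken within one hour either side of the anchor time. A pocketed dose leaves no opening of its own and so has no time stamp. It cannot be credited to the window without inventing a time.

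**The case against.** The strongest reply is that the arm bias depends on a mechanism the plan never states. Adjusting could mean excluding affected days or adding a covariate, and the additive arithmetic above would then not apply. This stands: crediting doses is the natural reading but not the only one.

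The reward is also narrow. It is one draw, after a missed threshold, in months 1 to 3. The threshold concerns timing, so a participant can miss it with full daily openings and gain nothing on Outcome 1 from credited doses. The 100% cap limits the upper end too: at the planning mean of 75%, average headroom is 25 points, below the largest assumed credit of 30. These points reduce the likely size.

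Raw openings are not free of bias either. They are what the prize rewards, they may be manipulated, and they would rise in the Incentives arm if incentives reduced pocketing. This stands as a cost of the fix.

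Analyst blinding limits result-driven choice of definition, but it does not remove bias already present in reports from unblinded participants.

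A reader might also infer that dose counts were withheld from the other arms, or that a wild card strictly required a pocketing report. The text supports neither outright. The count is described only for the Incentives arm, but the plan does not say it was not taken elsewhere. The link between wild card and report is implied by the stated aim of not penalising those who pocket doses.

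**Conclusion.** The definition conflict for Outcomes 1 and 2 is in the text, and the adjustment has no stated method. For Outcome 1, if the adjustment credits reported doses, the Incentives-only reward can produce an arm difference. Outcome 2 has the conflict but no prize motive, because the draws end at month three.

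The size is not established. Only the 15% comes from the documents; the doubling to 30% and the 10–30% credit are assumptions. On those assumptions the false gap is 1.5–4.5 points against another single arm and 0.75–2.25 points in the pooled contrast, or about a third of these if one month is affected.

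A reader might set the single-arm gap against the pooled 10.2-point benchmark and conclude that the bias is 15–45% of the detectable effect. That mixes two comparisons; like for like it is 13–38%, or 7–22% pooled. A reader might also infer that all four primary outcomes are biased by the prize, or that Outcomes 3 and 4 admit no adjustment at all. The documents support neither: the motive is confined to the intervention period, and dropping affected days would remain possible.

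The issue should be settled, but it does not invalidate the trial.

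**What to change.** Before arm results are seen:
- Keep the openings-only definition under Primary Outcomes 1 and 2 as the primary analysis in all arms.
- Change the sentence in Control Group: Usual Care so that the pocketing-adjusted version is a named sensitivity analysis under one written rule, applied by the blinded analyst and using only pocketing data recorded alike in every arm.
- If dose counts exist only for the Incentives arm, say so and do not use them to adjust that arm alone. Results states that data collection is complete, so a common question can no longer be added.
- Do not credit pocketed doses to Outcomes 3 and 4.
- Report pocketing rates by arm and both versions side by side. Call an Incentives effect on Outcome 1 robust only if the two agree in direction and approximate size.

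The cost is a change of wording and one extra analysis run. The downside is that unadjusted openings understate adherence among those who pocket doses, and they may favour the Incentives arm if incentives reduce pocketing. The side-by-side report would show this.
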